9.3 POPULATIONS FOR ANALYSES

The following populations will be used in the analyses of the Primary and Secondary endpoints in this study.

ITT Population: The intent to treat (ITT) population includes all subjects who received at least one hearing aid fitting strategy (*Vibe SF* or HCP fit) to evaluate. This population will be used for the Primary Objective hypothesis test. Missing values will be handled as described in Section 9.1.2.

mITT Population: The modified intent to treat (mITT) population includes all subjects in ITT population who have an endpoint for the analysis in question. The mITT population will be used for the analysis of the Secondary Objectives. No imputation of missing values will be done for these endpoints.

9.4 STATISTICAL ANALYSES

9.4.1 GENERAL APPROACH

Section 9 constitutes the statistical analysis plan (SAP) for this study.

The overall approach to this study is that it is an adaptive design with the adaptation being a change from a cross-over design to a parallel-arm design if the latter is necessary to avoid the interaction effects possible in a cross-over design. The high-level design with adaptation is:

1. The study begins with an intended sample size of 24 (28) subjects in a randomized cross-over design of SF first or HCP fit first. There is a washout period of 5 days intended to mitigate the order effect of the cross-over.
2. After 12 subjects have completed both hearing aid fittings and both Field tests, we will test for the order effect by looking for a significant interaction term in the analysis. (The methods of analysis are described below.)
 - a. If there is no interaction effect, then we continue with the cross-over design.
 - b. If there IS an interaction effect, then we will add subjects so that we have a minimum of 23 per arm (23+2, to account for drop-outs). (Note that we don't need 24 to balance the groups like we did in the cross-over design.) The new subjects will be randomized to SF or HCP fit for one period only. They don't cross over. Of the 12 existing subjects, we use only their Period 1 data; we ignore their data post cross-over.

NOTE: We will not suspend the trial while we analyze the data from the first 12. We will continue the cross-over study, but if we change to the parallel-arm design, we will ignore the Period 2 data (i.e., Field Test 2 data).

9.4.1.1 DESCRIPTIVE STATISTICS

This section describes the descriptive statistics that will be provided with each analysis. The statistics depend on the type of variable (endpoint) that is analyzed. All secondary objectives involve descriptive analyses only.

Descriptive statistics of subject demographics and baseline hearing status will be tabulated. No comparisons will be made because the same subjects serve as *Vibe SF* strategy and HCP fit strategy subjects in this cross-over study.

The descriptive statistics that will be presented will depend on the data type:

- 1) Continuous data will be summarized using n, mean, SD, minimum and maximum values.
- 2) Categorical data will be summarized using frequency and percentage.
- 3) Time-to-event data will be summarized using percentages at relevant time points, along with effective sample size and the 95% confidence interval.
- 4) Frequency (count) data will be summarized as a categorical variable if there are 5 or fewer values (see #2), or as a continuous variable if there are more than 5 distinct values (see #1).

9.4.1.2 CONTROL OF TYPE 1 ERROR

All hypothesis tests (of which there is only one compound test in this study, and that is for the Primary Effectiveness Objective) will be conducted at $\alpha=0.05$. Non-inferiority tests (the type of test in this study) are by nature one-tailed. The Primary hypothesis test will be conducted in 3 parts, as described in Section 9.1.1. To control Type 1 error associated with multiple tests, all 3 tests for the Primary Objective must have a p-value of 0.05 or smaller simultaneously.

Although the Secondary Objectives do not include any hypothesis testing, they will not be analyzed or reported unless the primary hypotheses pass (reject all 3 H_0 s).

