Secondary Preference Objective:

Fitting strategy (*Vibe SF* or HCP fit) preference reported by the subject.

Secondary Safety Objective:

To estimate the rate of adverse device effects (ADEs) when the subject is using the *Vibe SF* hearing aids.

Endpoints:**Primary Effectiveness Endpoint:**

Differences in the benefit scores on each of the three communication subscales as captured by the Abbreviated Profile of Hearing Aid Benefit (APHAB) after wearing each *Vibe SF* / Silk 1X HCP fit hearing aids for 14 days. For each subject, the endpoints are the individual 3 communication subscale differences between the HCP fit subscale (benefit) score and SF subscale (benefit) score:

- $\Delta EC(benefit)_{HCP\ fit} - \Delta EC(benefit)_{SF}$
- $\Delta BN(benefit)_{HCP\ fit} - \Delta BN(benefit)_{SF}$
- $\Delta RV(benefit)_{HCP\ fit} - \Delta RV(benefit)_{SF}$

Secondary Hearing Aid Benefit Endpoints:

1. The subject's sound quality, speech understanding and hearing aid satisfaction Ecological Momentary Assessment (EMA) ratings measured repeatedly under real-life conditions,
2. Speech-in-noise recognition performance as measured by the Quick Speech-In-Noise test (QuickSIN),
3. Hearing disability resulting from hearing loss quantified by the short form of the Speech, Spatial, and Qualities of Hearing Scale for clinical use: the SSQ-12 questionnaire.

Secondary Gain Selection Endpoint:

Individual frequency-specific gain comparison for the two different fitting strategies (*Vibe SF* and HCP fit) for each ear as measured with probe-mic real-ear measures (REM).

Secondary Preference Endpoint:

Fitting preference *Vibe SF* or HCP fit strategy. Subjects are asked which of the hearing aids they would prefer to keep using a 5-point Likert scale.

Secondary Safety Endpoint:

The number of adverse device effects (ADEs) in the time period when the subject is using the *Vibe SF* hearing aids.

Population: A minimum of 28 US subjects, within the age of 18 years and older, inexperienced or experienced hearing aid users with perceived mild-to-moderate hearing impairment. Potential subjects will be screened to confirm their bilateral sensorineural hearing loss.

Description of Sites/Facilities Enrolling Subjects: A single US University hearing aid research clinic. Potential subjects will be recruited locally by outreach at the investigator sites, local advertisements, social media advertisements and if needed professional recruiting service.

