Fitting (Vibe SF/HCP fit) preference reported by the subject.	
Fitting preference between the Vibe SF or HCP fit strategy.
 
Subjects will be asked to give their response on a 5-point Likert scale to the following question: Based on your listening experiences regarding speech understanding, sound quality and naturalness for both products, if you could keep one pair of these hearing aids, which would you choose?
 
Time point data collected: Cross-over Design: Visit 3
 
Parallel-arm Design: 12 Subjects: Visit 3
	Assessment of perceived hearing aid benefit should include the dimension of fitting preference of the subject.
Secondary Safety Objective		
To estimate the rate of safety when the subject is using the Vibe SF hearing aids.	
The number of adverse device effects (ADEs) in the time period when the subject is using the Vibe SF strategy hearing aids.
 
Time point data collected: Cross-over Design: Visit 1-3, Field Tests 1-2
 
Parallel-arm Design: 12 Subjects: Visit 1-3, Field Test 1-2 38 Subjects: Visit 1 and 2, Field Test 1
	Record, track and report device-related events as part of the risk management process for the SF strategy validation.

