9.1.2 SECONDARY

The secondary objectives do not include any hypothesis tests. However, they will not be analyzed unless the primary effectiveness hypothesis test passes (i.e., rejects all 3 null hypotheses).

Descriptive statistics will be reported on each endpoint by fitting strategy and overall, according to the list in Section 9.4.1.1. In addition, some endpoints require more detailed description. Additional descriptive statistics that will be reported are listed with the endpoints.

EMA Scores: Descriptive statistics of the scores will be reported by fitting strategy and measurement time for each real-life condition.

QuickSIN Scores: Descriptive statistics of the scores will be reported by fitting strategy and measurement time.

SSQ-12 Scores: Descriptive statistics of the scores will be reported by fitting strategy and measurement time for each subscale.

Gain Selection: Descriptive statistics of the probe-mic REM will be reported by fitting strategy and measurement time.

Fitting Preference: Descriptive statistics of the scores will be reported by fitting strategy and measurement time.

Safety Analyses: It is very unlikely that any device-related adverse events will be reported during this NSR device study. However, those that are reported will be tabulated by severity (mild-moderate-severe), seriousness (serious or non-serious) and relatedness (related, not related).

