9.4.3 ANALYSIS OF THE SECONDARY ENDPOINTS

Descriptive statistics will be reported on each endpoint by fitting strategy and overall, according to the list in Section 9.4.1.1. In addition, some endpoints require more detailed description. Additional descriptive statistics that will be reported are listed with the endpoints.

EMA Scores: Descriptive statistics of the scores will be reported by fitting strategy and measurement time for each real-life condition.

QuickSIN Scores: Descriptive statistics of the scores will be reported by fitting strategy and measurement time.

SSQ-12 Scores: Descriptive statistics of the scores will be reported by fitting strategy and measurement time for each subscale.

Protocol #: D00232675

08 September 2021

Gain Selection: Descriptive statistics of the probe-mic REM will be reported by fitting strategy and measurement time.

Fitting Preference: Descriptive statistics of the scores will be reported by fitting strategy and measurement time.

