9.4.4 SAFETY ANALYSES

It is very unlikely that any device-related adverse events (ADEs) will be reported during this NSR device study. However, those that are reported will be tabulated by severity (mild-moderate-severe), seriousness (serious or non-serious) and relatedness (related, not related).

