9.4.8 TABULATION OF INDIVIDUAL SUBJECT DATA

Data listings by subject will be provided to regulatory agencies.

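### All secondary summaries, with no exemption for the adverse-device-effect rate, are withheld unless the primary test passes, although they are descriptive and the gate protects no type I error

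*Combined protocol and SAP*

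**What the plan says.** The condition appears twice. Section 9.4.1.2, under control of type I error, reads: "Although the Secondary Objectives do not include any hypothesis testing, they will not be analyzed or reported unless the primary hypotheses pass". Passing means rejecting all three APHAB nulls. Section 9.1.2 says of the secondary objectives: "However, they will not be analyzed unless the primary effectiveness hypothesis test passes".

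The safety objective is one of the secondary objectives. The synopsis lists under that heading "To estimate the rate of adverse device effects (ADEs"; section 3 has it as "To estimate the rate of safety when the subject is using the" (Vibe SF hearing aids). Section 8.2 also labels device safety a secondary endpoint. Section 9.1.2 includes a safety paragraph among the analyses it covers.

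On the nature of these analyses, section 9.4.1.1 says: "All secondary objectives involve descriptive analyses only".

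The later analysis sections do not mention the condition. Section 9.4.3 says: "Descriptive statistics will be reported on each endpoint by fitting strategy and overall". Section 9.4.4 says of ADEs that "those that are reported will be tabulated by severity (mild-moderate-severe), seriousness (serious or non-serious) and relatedness (related, not related", essentially the same sentence as in section 9.1.2. Section 9.4.8 adds: "Data listings by subject will be provided to regulatory agencies".

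**The concern.** A gatekeeping rule is useful when secondary hypotheses are tested after the primary and the family-wise error rate must be held. Here there is nothing to hold: the study has one compound test, and every secondary analysis is a summary. What the rule does is decide, from the primary result, whether the summaries of real-ear gain, QuickSIN, SSQ-12, EMA, preference and ADEs are produced.

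The gate closes more often the worse the self-fit device performs. The planned summaries would then be missing when they are most needed. After a failed or borderline primary, gain and speech-in-noise results are the data that could show why, and the ADE rate is needed whatever the effectiveness result. Section 2.1 says the final report will be part of a 510(k) submission, so a report that lacks its planned safety summary because effectiveness failed would be hard to defend.

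**Working it through.** **1. What the gate covers.** Setting the sections side by side:

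| Section | Content | Conditional on the primary? |
|---|---|---|
| 9.1.2 | EMA, QuickSIN, SSQ-12, gain, preference, safety | Yes: analysis |
| 9.4.1.2 | Secondary objectives as a class | Yes: analysis and reporting |
| 9.4.3 | Secondary endpoint summaries | Not mentioned |
| 9.4.4 | ADE tabulation | Not mentioned |
| 9.4.2.1, 9.4.2.3 | APHAB descriptive statistics | No |
| 8.3, 8.4, 9.4.8, 10.1.5, 10.1.7 | Event capture, expedited reports, listings, monitor review, sponsor ADE records, final report | No |

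For the non-safety secondaries the gate is explicit. For the ADE summary, two sections withhold it by class and one describes it with no condition and no stated exemption.

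**2. What the gate protects.** There are no secondary tests, so the secondary type I error is 0 with or without the gate. The primary is controlled by requiring all three one-sided p-values to be 0.05 or smaller, and the gate does not enter into that.

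**3. How often it would close.**

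Inputs from section 9.2: margins 26 (EC), 27 (BN), 28 (RV); SD of the difference 34.4, 36.2, 36.1; one-sided alpha 0.05.

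Power for one subscale with true deficit d and n cross-over subjects: P(T > t(0.95, n−1)), where T is noncentral t with n−1 degrees of freedom and noncentrality (margin − d) / (SD/√n).

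*Check against the plan.* At n = 23 and d = 0 this gives EC 0.96892 and BN 0.96555; at n = 22, RV 0.96942. All three match the section 9.2 tables.

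*At n = 24* (critical value 1.714). With d = 0, EC noncentrality is 26 / (34.4/√24) = 3.70.

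The gate opens only if all three tests pass. The closure probability lies between 1 − smallest power (subscales fully correlated) and 1 − product of powers (independent subscales). Section 9.4.2.3 says only that the subscale benefits are likely correlated.

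| True deficit | Points (EC/BN/RV) | Power EC/BN/RV | Gate closed |
|---|---|---|---|
| 0 | 0 / 0 / 0 | 0.974 / 0.971 / 0.979 | 2.9% to 7.3% |
| 25% of margin | 6.5 / 6.75 / 7 | 0.853 / 0.845 / 0.869 | 15.5% to 37.4% |
| 50% of margin | 13 / 13.5 / 14 | 0.560 / 0.551 / 0.579 | 44.9% to 82.1% |

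For the first row: 1 − 0.9712 = 0.029, and 1 − 0.9742 × 0.9712 × 0.9793 = 0.073. Simulation with 200,000 trials per cell and an intermediate subscale correlation of 0.5 gives 6.3%, 30.2% and 69.3% for the three rows.

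*Parallel design, 23 per arm* (44 degrees of freedom, same standard error formula): 3.0% to 7.7% at zero deficit and 16.0% to 38.3% at 25% of margin.

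**4. Sensitivity to within-subject correlation.** The plan's SDs take the two fittings as uncorrelated within a subject; section 9.2 says there was no information on that correlation. If it is ρ, the SD of the difference is multiplied by √(1 − ρ). At n = 24:

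| ρ (assumed) | Zero deficit | 25% of margin | 50% of margin |
|---|---|---|---|
| 0 (plan) | 2.9% to 7.3% | 15.5% to 37.4% | 44.9% to 82.1% |
| 0.3 | 0.5% to 1.2% | 6.3% to 16.0% | 32% to 66% |
| 0.5 | 0.04% to 0.09% | 1.7% to 4.4% | 19% to 45% |

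At every ρ the gate closes more often as the deficit grows.

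**The case against.** Four points can be made for the plan.

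*Section 9.4.4 stands alone.* It has its own heading, apart from the secondary endpoints section, and says without condition that reported ADEs are tabulated. This is a fair reading, but the same sentence sits under the gate in section 9.1.2 and nothing says which section governs. What stands is that the plan is unclear on the ADE summary rather than plainly withholding it. That still needs correcting.

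*Safety information is not lost.* Event capture, expedited reports, medical monitor review, ADE records, the final report and subject listings all continue, as do APHAB descriptive statistics. This stands, and it limits the harm. But none of these is stated to be the planned ADE summary, and the APHAB statistics do not replace the gain or speech-in-noise summaries.

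*The gate stops favourable secondaries being promoted after a failed primary.* That is a legitimate aim, though not type I error control. Labelling the results descriptive serves it without withholding them, and the argument has no bearing on safety.

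*The closure percentages lean high.* This stands for the cross-over. The plan's zero within-subject correlation gives the upper end for any non-negative correlation, and the 25% and 50% deficits are illustrations; the plan assumes zero difference.

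**Conclusion.** The concern holds. As written, the plan makes the summary of every secondary objective depend on the primary result, exempts none of them, and leaves the ADE tabulation in doubt. The rule protects no alpha because there are no secondary tests.

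This is established by the text alone. The percentages only indicate how often the rule would bite: rarely if the devices are equivalent, and in a substantial share of trials if the self-fit device is moderately worse, including at half the margin, where it would still be non-inferior by the plan's own definition. They rest on the plan's SDs and margins, 24 evaluable subjects (or 23 per arm), assumed true deficits, and the full range of subscale correlation from 0 to 1.

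The primary inference is unaffected. This is a change that should be made, not one on which the trial's validity turns.

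**What to change.** Delete the gating sentence in section 9.1.2 and the one in section 9.4.1.2. Add one sentence stating that the analyses in sections 9.4.3 and 9.4.4 are performed and reported whatever the primary result, with secondary results labelled descriptive.

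Sample size, data collection and the one-sided 5% rule on the three primary tests do not change. Because section 9 is the SAP and part of the protocol, the edit is a protocol amendment and needs IRB review and approval before it is implemented, as the statement of compliance requires.

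### The rule holding back secondary objectives unless the primary test passes makes no exception for safety, so read literally the aggregate ADE summary is dropped when Vibe SF fails

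*Combined protocol and SAP*

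**What the plan says.** The synopsis (1.1) lists a Secondary Safety Objective: "To estimate the rate of adverse device effects (ADEs) when the subject is using the" Vibe SF hearing aids. Section 3 lists it among the secondary objectives too, and 8.2 calls it a secondary endpoint.

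The hold-back rule appears twice. Section 9.1.2 says of the secondary objectives that "they will not be analyzed unless the primary effectiveness hypothesis test passes", meaning that all three APHAB nulls are rejected. Section 9.4.1.2 extends this to reporting: "Although the Secondary Objectives do not include any hypothesis testing, they will not be analyzed or reported unless the primary hypotheses pass".

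The safety analysis is also described twice. Section 9.1.2, under the rule, has an item that begins "Safety Analyses: It is very unlikely that any device-related adverse events will be reported during this NSR device study" and goes on to promise a tabulation of any that occur. Section 9.4.4, which stands apart from the secondary endpoints in 9.4.3, says that "those that are reported will be tabulated by severity (mild-moderate-severe), seriousness (serious or non-serious) and relatedness (related, not related"). It mentions neither the rule nor an exemption.

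Two other places bear on the fix. Section 9.3 assigns the secondary objectives to the mITT set, meaning ITT subjects "who have an endpoint for the analysis in question". On a switch to parallel arms, 9.4.1 says: "Of the 12 existing subjects, we use only their Period 1 data; we ignore their data post cross-over". The Section 3 safety row for that design reads "12 Subjects: Visit 1-3, Field Test 1-2".

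**The concern.** Making secondary efficacy claims wait for the primary result is ordinary practice. Safety is different: a failed non-inferiority test is when a reader most wants to know whether the self-fitted device also caused discomfort or other device effects. As written, the rule makes the planned safety summary depend on the efficacy result.

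The rule sits under the heading on control of Type 1 error, yet it controls none here. Section 9.4.1.1 makes all secondary objectives descriptive, and 9.4.1.2 says the study has a single compound test. Holding back an ADE table saves no alpha.

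Section 2.1 says the final study report will go into the 510(k) submission, so whether that report must contain a safety summary should not be left to interpretation.

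**Working it through.** **The text.**

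1. The Vibe SF ADE objective is a secondary objective (1.1, 3, 8.2).
2. Secondary objectives are neither analysed nor reported unless all three primary nulls are rejected (9.1.2, 9.4.1.2).
3. Neither section makes an exception, and 9.1.2 lists the safety analyses among the items it covers.
4. Section 9.4.4 promises the tabulation without condition. Its wording nearly repeats the safety item in 9.1.2, so the wording alone cannot signal an exemption.

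Steps 1 to 3 drop the summary after a failed primary. Step 4 makes that conclusion contestable without removing it.

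**How often the primary would fail.** Inputs from 9.2 (power tables): one-sided alpha 0.05; margins 26 (EC), 27 (BN), 28 (RV); SD of the paired difference 34.4, 36.2, 36.1; true difference d = 0; within-subject correlation 0. The 9.2 parameter table has the BN and RV SDs the other way round, which moves the results below by no more than 0.1 percentage point.

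Power for one subscale = P(T > t(0.95, n-1)), where T is noncentral t with n-1 df and noncentrality (margin - d) / (SD/√n).

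*The plan's own figures:* EC n=23 gives 0.9689, RV n=22 gives 0.9694, BN n=23 gives 0.9655. All three match 9.2.

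*At the planned 24 completers, d = 0:* the critical value is 1.714.
- EC: 26/(34.4/√24) = 3.70, power 0.974
- BN: 27/(36.2/√24) = 3.65, power 0.971
- RV: 28/(36.1/√24) = 3.80, power 0.979

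All three must pass. If the tests are fully dependent, failure = 1 - smallest power = 1 - 0.971 = 2.9%. If they are independent, failure = 1 - product = 1 - 0.927 = 7.3%. If all 28 complete, the same steps give 1 - 0.986 = 1.4% to 1 - 0.965 = 3.5%.

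*If Vibe SF is truly worse.* The differences of 5 and 10 points and the correlation of 0.5 are assumptions; the documents give no value for either. A correlation of 0.5 multiplies the SD of the difference by √0.5. The parallel-arm row uses a two-sample t-test with 44 df and the per-arm SDs from 9.2 (24.3, 25.6, 25.5).

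| Design | d = 0 | d = 5 | d = 10 |
|---|---|---|---|
| Cross-over, n=24, correlation 0 (plan) | 2.9-7.3% | 10.7-26.7% | 28.6-60.5% |
| Cross-over, n=24, correlation 0.5 | under 0.1% | 0.7-1.9% | 6.9-16.9% |
| Parallel arms, 23 per arm | 3.0-7.7% | 11.0-27.4% | 29.0-61.3% |

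Each range runs from fully dependent to independent tests.

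**The case against.** **Section 9.4.4 may already be the exemption.** Section 9.4.3 covers the secondary endpoints and omits safety. Section 9.4.4 stands alone and is unconditional, and the Section 3 rationale for the safety row commits to reporting device-related events. That is fair evidence of intent, and it rules out saying that the plan clearly means to withhold safety. It does not settle the matter, because 9.1.2 places the same analysis under the rule.

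**Little safety information is lost.** This largely stands. All adverse events go on the case report form (8.3.4), expedited reports go to the IRB and FDA (8.3.6, 8.4.2), the medical monitor reviews every event (10.1.5), and subject listings go to regulators (9.4.8). A Study Safety Plan outside these documents may say more. A reader might infer that safety data are suppressed after a failed trial; the documents do not support that. Only the planned aggregate summary is at risk.

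**The failure rate is not the chance of losing an ADE finding.** Correct. At an assumed ADE risk of 5% per wearer, the chance of at least one among 28 wearers is 1 - 0.95^28 = 0.76. Assuming independence, failure together with at least one ADE has probability 0.029 × 0.76 to 0.073 × 0.76, about 2-6%. Still, a reported count of zero is also a safety result, and it would be dropped too.

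**The Period 2 rule need not touch safety.** A reader might infer from 9.4.1 that a switch discards Vibe SF exposure for the six HCP-first subjects who wear it only in Field Test 2. The documents point the other way. Section 9.4.2.2 ties the restriction to the analysis of the parallel-arm data, Section 3 takes fitting preference solely from the 12 crossed-over subjects at Visit 3, and the safety row lists both field tests. This is loose wording to tidy, not a second defect.

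**Conclusion.** The point holds as a gap in the reporting rule. Sections 9.1.2 and 9.4.1.2, taken at their word, drop the aggregate Vibe SF ADE summary when the primary fails; 9.4.4 makes the plan inconsistent rather than clear. The textual finding rests on no numerical assumption.

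Its reach is modest. On the plan's cross-over assumptions (no true difference, zero correlation, 24 completers, the t-test used for sizing) the primary fails in about 3-7% of trials. The higher rates in the table depend on assumed true differences, and a positive within-subject correlation would lower the cross-over rates. The primary result, sample size and alpha are untouched. It should be corrected, because it is cheap and the rule serves no purpose for safety, but it does not threaten the trial.

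Exempting 9.4.4 alone would not deliver the stated objective. The objective is a rate, the endpoint is a number of events, and 9.4.4 plans only a tabulation, so a denominator is needed. The mITT set is a poor choice: 9.3 defines it by having an endpoint, while 9.4.1.3 equates it with subjects free of major protocol violations.

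**What to change.** - **9.1.2 and 9.4.1.2:** state that the safety objective is exempt from the hold-back rule and that 9.4.4 is reported whatever the primary result.
- **9.3 and 9.4.4:** report the number of ADEs and their rate over all subjects fitted with Vibe SF, including those who later withdraw or violate the protocol, in place of the mITT set.
- **9.4.1:** say that ignoring Period 2 data after a switch applies to the primary comparison and not to safety, in line with the Section 3 safety row.

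The cost is a few sentences. No new data, visits or staff are needed, and no alpha is spent. The downside is that small descriptive counts may be over-read, above all beside a failed primary result; a line noting that they are descriptive would help.
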